4.2.3. Disease Control Rate (DCR)

4.2.3.1. Definition

DCR is defined as the proportion of patients who achieve SD for a minimum of 12 weeks, or better (i.e., SD for a minimum of 12 weeks, MR, PR, VGPR, CR, sCR).

4.2.3.2. Analysis Methods

The rate of DCR and the 2-sided, exact 95% CI will be calculated using the mITT population.

As supportive analyses, DCR rate and 95% CI will be calculated:

- Using the BCLPD-ref, CLPD-ref, BCPD-ref, and CPD-ref populations respectively, if sufficient data exist

4.2.4. Progression Free Survival (PFS)

4.2.4.1. Definition

PFS is defined as the duration from start of study treatment to time of IRC-determined PD or death from any cause, whichever occurs first. Please refer to Table 4-1 for details on PFS outcome status (PFS event vs. censored) and date definition. Unless otherwise specified, PD status refers to confirmed PD or PD by unambiguous criteria based on IRC assessment. If PD is based on 2 independent samples on an applicable disease parameter, date of PD refers to the earlier date of the 2 independent samples.

4.2.4.2. Analysis Methods

A duration is calculated as end date – start date + 1. For instance, if a PFS event occurs, then PFS time (in days) is defined as event date – start date of study treatment + 1. If a censoring event occurs, then PFS time is defined as the censoring date – start date of study treatment + 1.

Table 4-1 PFS outcome and censoring definition

Situation	Date of event or censoring	Outcome
No adequate post-baseline disease status assessment unless death occurs prior to first post-baseline assessment	Start of study treatment	Censored
Death before IRC-determined PD without a gap of 65 days or longer before death	Death date	PFS event
IRC-determined PD without a gap of 65 days or longer before progression	Date of PD	PFS event
No IRC-determined PD or death on or before 
 a. database cut, b. withdrawal of informed consent, c. lost to follow-up, d. documented treatment discontinuation e. start of new MM treatment, whichever occurs first 	Date of last adequate disease assessment prior to the earliest occurrence of the events (a. – e.) listed in the left column	Censored
No IRC-determined PD or death before a gap of 65 days or longer, which corresponds to 2 or more consecutively missed scheduled disease status assessment	Date of last adequate disease assessment prior to the gap	Censored

Median PFS with 95% CI will be estimated based on the Kaplan-Meier method. The Kaplan-Meier curve for PFS will be provided.

The following supportive analyses will be conducted:

- PFS based on Investigator assessment
- PFS in the BCLPD-ref, CLPD-ref, BCPD-ref, and CPD-ref populations respectively, if sufficient data exist

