4.1. PRIMARY EFFICACY ENDPOINT

4.1.1. Definition

The primary endpoint is ORR which is defined as the proportion of patients who achieve a confirmed PR or better (i.e., PR, VGPR, CR, or sCR), as assessed by the IRC, during or after the study treatment, before documented disease progression or initiating a new MM treatment.

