4.2.1. Duration of Response (DOR)

4.2.1.1. Definition

DOR is defined for patients with a confirmed PR or better as the duration from first observation of at least PR to time of IRC-determined PD or death due to disease progression, whichever occurs first. The censoring method for DOR is the same as the censoring method for TTP in Table 4-2.

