4.2.5.2. Analysis Methods

Table 4-2 TTP outcome and censoring definition

Situation	Date of event or censoring	Outcome
No adequate post-baseline disease status assessment unless death due to disease progression occurs prior to first post-baseline assessment	Start of study treatment	Censored
Death due to disease progression before IRC-determined PD without a gap of 65 days or longer before death	Death date	TTP event
IRC-determined PD without a gap of 65 days or longer before progression	Date of disease progression	TTP event
No IRC-determined PD or death due to disease progression on or before 
 1. Death due to reasons other than disease progression 2. database cut, 3. withdrawal of informed consent, 4. lost to follow-up, 5. documented treatment discontinuation 6. start of new MM treatment, whichever occurs first 	Date of last adequate disease assessment prior to the earliest occurrence of the events (1. – 6.) listed in the left column	Censored
No IRC-determined PD or death due to disease progression before a gap of 65 days or longer, which corresponds to 2 or more consecutively missed scheduled disease status assessment	Date of last adequate disease assessment prior to the gap	Censored

Median TTP with 95% CI will be estimated based on the Kaplan-Meier method. The Kaplan-Meier curve for TTP will be provided.

The following supportive analyses will be conducted:

- TTP based on Investigator assessment
- TTP in the BCLPD-ref, CLPD-ref, BCPD-ref, and CPD-ref populations respectively, if sufficient data exist
- TTP on most recent prior therapy

Note that MM response assessment is scheduled to be conducted every 28 days. The maximum allowed gap length of 64 days is selected to correspond to 2 scheduled response assessments while allowing small deviations from target dates.

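### SAP Tables 4-1 and 4-2 score progression or death soon after study drug stops both as an event and as censored, with no stated precedence and no defined stop date

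*SAP*

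**What the plan says.** SAP 4.2.4.2, Table 4-1 (PFS), has five rows.

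- Row 1 censors at the start of treatment: "No adequate post-baseline disease status assessment unless death occurs prior to first post-baseline assessment".
- Row 2 makes this an event at the death date: "Death before IRC-determined PD without a gap of 65 days or longer before death". Row 3 does the same for IRC-determined PD. Neither requires the patient to be on treatment.
- Row 4 applies to a patient with no PD or death on or before the first of five triggers. Item d is "documented treatment discontinuation". The censoring date is the "Date of last adequate disease assessment prior to the earliest occurrence of the events".
- Row 5 censors before "a gap of 65 days or longer, which corresponds to 2 or more consecutively missed scheduled disease status assessment".

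Table 4-2 (TTP) repeats this. Its event rows count PD and death due to progression, and the discontinuation trigger is item 5. For DOR, SAP 4.2.1.1 says: "The censoring method for DOR is the same as the censoring method for TTP in Table 4-2". SAP 4.2.2.1 takes the TTP censoring date for duration of clinical benefit.

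The note under Table 4-2 ties the gap rule to 28-day visits: "The maximum allowed gap length of 64 days is selected to correspond to 2 scheduled response assessments while allowing small deviations from target dates".

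SAP 2.3 defines a date of last study treatment, but neither table refers to it. Footnote 15 of the schedule of assessments plans disease assessments every 3 months for a year after discontinuation, if possible, in order to assess durability of response. ORR (SAP 4.1.1) counts responses "during or after the study treatment, before documented disease progression or initiating a new MM treatment".

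**The concern.** Two programmers following the tables could score the same patient differently. The words on which trigger comes first rank only the items within row 4. They do not rank row 4 against rows 2 and 3. The surrounding text does not settle it either: SAP 4.2 and 4.2.4.1 treat death from any cause as a PFS event, which is at odds with censoring a death because drug had stopped.

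Under either reading, the off-treatment assessments planned to measure durability contribute almost nothing to DOR. SAP section 4 calls DOR and duration of clinical benefit key secondary endpoints, and SAP 1.6 plans a DOR update before the NDA. In an open-label single-arm trial, censoring rules should leave no choice to be made once the data are known.

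**Working it through.** **1. The plan's own gap figure.** Visits are 28 days apart, with a window of ±2 days at each end.

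| Visits missed | Gap in days |
|---|---|
| 0 | 24–32 |
| 1 | 52–60 |
| 2 | 80–88 |

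A cut at 64/65 days separates one missed visit from two, so the figure is reproduced for the on-treatment schedule.

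**2. One patient under both rows (constructed example).** First PR Day 29, last on-treatment assessment Day 85, last dose Day 88, EoT visit Day 98, death due to progression Day 120. Duration = end − start + 1 (SAP 4.2.4.2).

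| Rule | PFS | DOR |
|---|---|---|
| Row 2 (gap 120 − 98 = 22 days, or 120 − 85 = 35) | event, 120 days | event, 120 − 29 + 1 = 92 days |
| Row 4 | censored, 85 days | censored, 85 − 29 + 1 = 57 days |

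Row 4 requires an assessment before the trigger, so the censoring date is Day 85 whether the stop date is the last dose or the EoT visit.

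**3. Where the undefined stop date matters.** EoT may fall up to 14 days after the last dose. PD first seen at EoT is after discontinuation if that means the last dose, and the rows then conflict. If it means the EoT date, PD falls on the trigger date and they do not.

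**4. The gap rule applied to follow-up.** EoT is 0 to 14 days after the last dose, and follow-up visits are 3 months apart, ±14 days. Assumptions: the first visit is timed from the last dose, every day within a window is equally likely, and a month-length convention applies. Day combinations 65 days or more apart:

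| 3 months taken as | EoT to first follow-up | Follow-up to follow-up |
|---|---|---|
| 84 days | 390/435 = 89.7% | 796/841 = 94.6% |
| 91 days | 432/435 = 99.3% | 838/841 = 99.6% |
| 92 days | 434/435 = 99.8% | 840/841 = 99.9% |

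A fully compliant patient whose PD is first found at a 3-monthly visit is therefore almost always censored, even if the event rows govern. PD at an unscheduled assessment, or a progression death, within 64 days of the last assessment would still count.

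**5. A response first seen in follow-up (constructed example).** Last on-treatment assessment Day 57, last dose Day 60, EoT Day 70, first PR at follow-up on Day 151. Row 4 censors at Day 57: DOR = 57 − 151 + 1 = −93 days. Row 5 (gap 151 − 70 = 81 days) censors at Day 70: DOR = 70 − 151 + 1 = −80 days. Only a later PD or progression death scored as an event would avoid this.

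**6. Scale for DOR.** Protocol Table 3 gives an ORR of 20% (6 of 30) in Part 1 penta-refractory patients; 20% of 122 is about 24 responders. With a median of about 5 months (protocol synopsis), exponential durations and 24 events, sampling limits are 5 × exp(±1.96/√24) = 3.4 to 7.5 months.

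A simulation compared the two readings in 20 scenarios: 10–40% stopping without PD, and a hazard after stopping 0.67 to 3 times that before. It assumed exponential PD times with a true median of 5 months, the scheduled visits with 91-day quarters, and PD dated at the detecting visit. With PD only:

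| Stop date | Patients scored differently | Of 24 responders | Same median |
|---|---|---|---|
| Last dose | 0.2–3.3% | 0.1–0.8 | 19 of 20 scenarios |
| EoT | 0.0–0.1% | under 0.1 | 20 of 20 scenarios |

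The largest difference in medians was one visit interval, 28 days or 0.9 months.

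**The case against.** The strongest reply is that row 4 is meant to govern. It is conditioned on time, and its triggers include the database cut and new myeloma treatment. If rows 2 and 3 overrode it, PD after the cut or after another therapy would count and the triggers would do little. This is the more natural reading. On it, censoring at discontinuation is a choice of estimand that the sponsor may make, and the gap-rule problem in follow-up does not arise. What stands is that the SAP does not say so, that this reading conflicts with its statement that any death is a PFS event, and that it excludes all follow-up assessments from DOR.

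It can also be said that discontinuation is recorded in the eCRF, and that PD is dated to the earlier of two samples and so will often precede the stop. Both points narrow the stop-date problem, but neither supplies a date rule.

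A reader might infer more than the documents support:

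- **That many early deaths are caught in PFS.** Seven of 30 Part 1 penta-refractory patients were non-evaluable, and 7/30 × 122 is about 28. The documents do not say why they were non-evaluable or how many died after stopping, and row 1 specifically exempts early deaths from its censoring. This is not an estimate of the number affected.
- **That several responders would be scored differently.** If half of post-stop events were progression deaths without earlier IRC-determined PD, the simulated share reaches 12.4% (3.0 of 24) with the last-dose date. Nothing in the documents supports that share.

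**Conclusion.** The tables contradict themselves for PD, or a qualifying death, that occurs after study drug stops but within 64 days of the last adequate assessment. The stop date is not tied to a definition. Whichever row governs, 3-monthly assessments contribute almost nothing to PFS, TTP, DOR or duration of clinical benefit: none if row 4 governs; if rows 2 and 3 govern, PD first found at about 90% to over 99% of compliant visits is censored, given the assumed month length and uniform timing. A negative DOR is possible, probably rarely.

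It would be tempting to conclude that the reported DOR will be biased or that the trial's main conclusion is at risk. The documents do not support that. The primary ORR test does not use these rules, DOR is summarised descriptively, and follow-up still feeds ORR, TTNT and OS. Under the stated assumptions any shift in the median is at most 0.9 months, within sampling limits of 3.4 to 7.5 months. This is a fault in the rules, worth correcting because it is cheap and DOR is a key secondary endpoint.

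**What to change.** - **Both tables:** make the rows mutually exclusive, state which takes precedence, and tie treatment discontinuation to a defined date.
- **DOR and duration of clinical benefit:** apply gap and censoring rules only from the first response date onwards, so that no duration can be negative.
- **Main analysis and sensitivity:** keep the sponsor's chosen rule as the main analysis. Add one pre-specified DOR sensitivity analysis that counts off-treatment PD and progression deaths up to the start of new therapy. In it, define the gap as two missed visits on the schedule in force: 28-day on treatment, 3-monthly in follow-up.

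The cost is SAP wording and minor programming. The follow-up visits are already scheduled, though only where possible. PD found at 3-monthly visits is dated more coarsely, and the sensitivity estimate may be less favourable than the main one.

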4.2.5. Time to Progression (TTP)

4.2.5.1. Definition

TTP is defined as the duration from start of study treatment to time of IRC-determined PD or death due to disease progression, whichever occurs first. Please refer to Table 4-2 for details on TTP outcome status and date definition. Unless otherwise specified, PD assessment refers to assessment determined by IRC. But for the cause of death, disease progression refers to investigator assessment as specified on the eCRF death report page.

4.2.5.2. Analysis Methods

Table 4-2 TTP outcome and censoring definition

Situation	Date of event or censoring	Outcome
No adequate post-baseline disease status assessment unless death due to disease progression occurs prior to first post-baseline assessment	Start of study treatment	Censored
Death due to disease progression before IRC-determined PD without a gap of 65 days or longer before death	Death date	TTP event
IRC-determined PD without a gap of 65 days or longer before progression	Date of disease progression	TTP event
No IRC-determined PD or death due to disease progression on or before 
 1. Death due to reasons other than disease progression 2. database cut, 3. withdrawal of informed consent, 4. lost to follow-up, 5. documented treatment discontinuation 6. start of new MM treatment, whichever occurs first 	Date of last adequate disease assessment prior to the earliest occurrence of the events (1. – 6.) listed in the left column	Censored
No IRC-determined PD or death due to disease progression before a gap of 65 days or longer, which corresponds to 2 or more consecutively missed scheduled disease status assessment	Date of last adequate disease assessment prior to the gap	Censored

Median TTP with 95% CI will be estimated based on the Kaplan-Meier method. The Kaplan-Meier curve for TTP will be provided.

The following supportive analyses will be conducted:

- TTP based on Investigator assessment
- TTP in the BCLPD-ref, CLPD-ref, BCPD-ref, and CPD-ref populations respectively, if sufficient data exist
- TTP on most recent prior therapy

Note that MM response assessment is scheduled to be conducted every 28 days. The maximum allowed gap length of 64 days is selected to correspond to 2 scheduled response assessments while allowing small deviations from target dates.

4.2.6. Time to Next Treatment (TTNT)

4.2.6.1. Definition

TTNT is defined as the duration from start of study treatment to start of next anti-MM treatment or death, whichever occurs first. For patients without an event, their follow-up time will be censored at the date of discontinuation from study, or last participating visit.

4.2.6.2. Analysis Methods

Median TTNT with 95% CI will be estimated based on the Kaplan-Meier method. The Kaplan-Meier curve for TTNT will be provided.

The following supportive analyses will be conducted:

- TTNT in the BCLPD-ref, CLPD-ref, BCPD-ref, and CPD-ref populations respectively, if sufficient data exist
- TTNT on most recent prior therapy

4.2.7. Overall Survival (OS)

4.2.7.1. Definition

OS is defined as the duration from start of study treatment to death from any cause. If death event did not occur during the follow-up period, the patient is censored at the date of discontinuation from the study, or date of last participating visit (e.g., a telephone contact with patient status being alive), or database cut date, whichever is earlier.

4.2.7.2. Analysis Methods

The proportion of patients with death event and the 2-sided, exact 95% CI will be calculated using the mITT population. Median OS time with 95% CI will be estimated based on the Kaplan-Meier method. The Kaplan-Meier curve for OS will be provided.

The following supportive OS analyses will be conducted:

- Using the BCLPD-ref, CLPD-ref, BCPD-ref, CPD-ref populations respectively
- Using the all penta-ref, high-risk, EE, PP, Part 1 – Quad, Part 1 – Penta, respectively, if sufficient data exist

- The same as in primary OS analysis except additional censoring at the start date of a new MM treatment
- In patients with R-ISS for MM stage I, II, and III respectively, if sufficient data exist
- In US vs. non-US patients, if sufficient data exist
- In FLC MM vs. non-FLC MM patients, if sufficient data exist
- In patients with a best response of confirmed PR or better
- In patients with a best response of confirmed MR or better
- In patients with a best response of confirmed MR
- In patients with a best response of SD or worse (including patients whose disease is not evaluable)

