
Concomitant Medications:
 
To minimize nausea, unless contraindicated, all patients should receive 5-hydroxytryptamine (5-HT3) antagonists (e.g., ondansetron 8 mg or equivalent) starting on Day 1 before the first dose of selinexor and continued 2-3 times daily, as needed. Alternative anti-emetic agents should be used if the patient does not tolerate 5-HT3 antagonists. Additional anti-nausea and anti-anorexia agents may be given as needed (per National Comprehensive Cancer Network® [NCCN] Clinical Practice Guidelines® for Antiemesis and NCCN Clinical Practice Guidelines® for Palliative Care). Patients will also receive therapy as needed to mitigate selinexor side effects, as part of best supportive care. Blood product transfusions, antimicrobials, and (as appropriate) growth factors including granulocyte colony-stimulating factors for neutropenia, erythropoietins for anemia, and/or platelet-stimulating factors for thrombocytopenia are also permitted.
 
Patients may continue their baseline medication(s). Medications to treat concomitant diseases such as diabetes, hypertension, etc., are allowed. Patients will also receive concomitant medications that are medically necessary as standard care to treat symptoms, AEs and intercurrent illnesses. Patients may receive red blood cell or platelet transfusions, or blood growth factors, if clinically indicated, per institutional guidelines.
 
Concurrent therapy with any other approved or investigational anti-cancer therapy is not allowed. Other investigational agents should not be used during the study.
		

Study Numbers:
 
Approximately 210 patients will be enrolled overall, including 79 patients (with quad-refractory MM and penta-refractory MM) in Part 1 and ~130 patients (with penta-refractory MM only) in Part 2 (to achieve the target population size of N = 122 for the primary efficacy analysis).
		

Study Duration:
 
The enrollment period for this study is expected to be approximately 24 months. There is no maximum treatment duration for the study or pre-defined number of treatment cycles
		

Sponsor: Karyopharm Therapeutics Inc.	Investigational Product: Selinexor (KPT-330)	Developmental Phase: Phase 2b

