1.4. STUDY PLAN

For each patient that signs the informed consent, the study consists of:

- Screening/baseline visit: occurs within 21 days prior to receiving the 1st dose of study treatment
- Treatment period: expected to be up to 12 months, but there is no maximum treatment duration. Patients will be treated until disease progression, death, toxicity that cannot be managed by standard care, or withdrawal from study, whichever occurs first
- Follow-up period: up to 12 months after last dose of study treatment, patients will be contacted approximately every 3 months for durability of response and survival follow-up

The End of Study (EoS) will occur when all patients have completed the 12-month follow-up period (i.e., when the last patient has expired, been followed for 12 months after last dose of study treatment, been lost to follow-up, or has withdrawn consent, whichever occurs first).

Please refer to Table 7-1 for detailed schedule of assessment and study activities.

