1.6. DATABASE LOCK

The primary analysis will be performed after all patients have completed the Cycle 2 MM Assessments, and will include a formal snapshot of database and analyses of efficacy, safety, and PK data. A clinical study report (CSR) will be prepared after the primary analysis. The data cut date for IRC-based MM response assessment may be later than the data cut date for other data points. All data points presented to IRC members for their assessment have been source verified.

At the time of the database snapshot for the primary analysis, the median DOR estimate may not be estimable with limited follow-up time. Therefore, an efficacy update on ORR and DOR among the Part 2 patients with penta-refractory MM will be provided before the submission of the New Drug Application (NDA) package.

The final analysis will be performed at the end of the study after all patients have completed the 12-month follow-up period (i.e., when the last patient has expired, been followed for 12 months after last dose of study treatment, been lost to follow-up, or has withdrawn consent, whichever occurs first). There will be a formal database lock and analyses of efficacy and safety data. A final CSR will be prepared summarizing the results from the full analysis.

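### The overall-survival death proportion carries an exact binomial interval but no time point, although follow-up is unequal and censored

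*SAP*

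**What the plan says.** SAP 4.2.7.2 opens the OS methods with this line: "The proportion of patients with death event and the 2-sided, exact 95% CI will be calculated using the mITT population". It then plans the standard analysis, "Median OS time with 95% CI will be estimated based on the Kaplan-Meier method", and the Kaplan-Meier curve.

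SAP 4.2.7.1 sets the censoring. If no death occurred, "the patient is censored at the date of discontinuation from the study, or date of last participating visit", or at the database cut, whichever is earlier.

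Follow-up length comes from three places:
- SAP 1.6: "The primary analysis will be performed after all patients have completed the Cycle 2 MM Assessments".
- Protocol synopsis, Study Duration: "The enrollment period for this study is expected to be approximately 24 months". The Part 2 share of that period is not given.
- SAP 1.4: treatment is "expected to be up to 12 months, but there is no maximum treatment duration". After that comes "Follow-up period: up to 12 months after last dose of study treatment".

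For time-to-event data, Protocol 13.1.1 and 13.3.4 plan Kaplan-Meier quartiles with intervals, and 13.1.1 adds the percentage censored. They plan no binomial interval on the proportion of events. The SAP sections on duration of response, PFS, TTP and time to next treatment plan none either. Neither document plans a Kaplan-Meier survival probability at a fixed time.

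**The concern.** An exact binomial interval needs a settled yes/no outcome over the same exposure for every patient. Here a patient censored alive after two months and one known alive after a year both count as non-deaths, and so does a patient who withdrew alive.

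The resulting percentage has no time horizon, and its interval suggests a precision about mortality that it does not have. A reader of the study report could take it as a mortality rate and set it beside another study's rate. It could also be compared between analysis sets with different follow-up. SAP 4.2.7.2 lists supportive OS analyses in the Part 1 populations, which enrolled earlier. If the proportion is repeated there, Part 1 would tend to show more deaths simply from longer observation.

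If the Kaplan-Meier median or its upper limit is not reached at the snapshot, the crude proportion could be the only OS estimate with a complete interval in the primary report.

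**Working it through.** **Nothing to reproduce.** The documents state no assumed OS median, death rate or event count. The check asks what the planned proportion would estimate.

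**Inputs from the documents.** N = 122 (Protocol synopsis, Study Numbers: "to achieve the target population size of N = 122 for the primary efficacy analysis"). The primary snapshot follows the Cycle 2 assessments, about 1 to 2 months after the last patient starts; 2 months is used.

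**Assumptions not in the documents.** OS is exponential with median 6, 9 or 12 months. Part 2 accrual is uniform over A = 9, 12 or 24 months. Loss to follow-up is 0% or 15% a year and independent of survival.

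**Formula.** With rate λ = ln 2 / median, and follow-up uniform from L to L + A months without loss, the expected crude proportion is

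p = 1 − [exp(−λL) − exp(−λ(L + A))] / (λA).

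This average risk over the follow-up distribution is what the exact interval covers. True mortality by month t is 1 − exp(−λt).

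**Median 9 months, L = 2.** λ = 0.6931/9 = 0.07702 and exp(−2λ) = 0.8572.
- A = 9: 1 − (0.8572 − 0.4286)/0.6931 = 0.382
- A = 12: 1 − (0.8572 − 0.3402)/0.9242 = 0.441
- A = 24: 1 − (0.8572 − 0.1350)/1.8484 = 0.609

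True mortality is 0.370 at 6 months and 0.603 at 12 months in all three.

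**Range over the assumed medians** (simulation, 4,000 trials of 122 patients per scenario, no loss):

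| Median OS | True, 6 mo | True, 12 mo | Crude, A = 9 | Crude, A = 12 | Crude, A = 24 |
|---|---|---|---|---|---|
| 6 mo | 50.0% | 75.0% | 50.6% | 57.1% | 73.2% |
| 9 mo | 37.0% | 60.3% | 38.2% | 44.1% | 61.0% |
| 12 mo | 29.3% | 50.0% | 30.4% | 35.7% | 51.9% |

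**Loss to follow-up.** With 15% yearly loss and median 9 months, the crude figure falls to 36.6%, 41.7% and 56.0% for the three accrual lengths. Survival has not changed; patients lost alive are counted as non-deaths.

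**Cut date.** With median 9 months and A = 12, moving the cut from 2 to 6 or 12 months after last entry gives 0.441, 0.589 and 0.741. This assumes everyone is followed to the cut.

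**Coverage of the exact 95% interval, read as fixed-time mortality** (all medians, with and without loss):

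| Accrual | For 6-month mortality | For 12-month mortality |
|---|---|---|
| 9 mo | 95.5–96.4% | 0–1% |
| 12 mo | 69–87% | 0.3–13.5% |
| 24 mo | 0.1–2.3% | 93–96% without loss, 62–94% with loss |

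Which time point the interval matches, if any, is decided by accrual and loss.

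**Kaplan-Meier in the same data.** The estimated 6-month risk averaged 0.367–0.373 against a true 0.370 for median 9 months, over every accrual and loss scenario. For medians 6 and 12 months it was 0.499–0.505 (true 0.500) and 0.291–0.293 (true 0.293).

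**The case against.** The case for leaving the line alone is substantial.

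- **Censoring is already handled.** The next two sentences of SAP 4.2.7.2 give the Kaplan-Meier median with interval and the curve. A reader might infer that OS is analysed only by a crude proportion; the section itself refutes that. This stands.
- **The label is accurate.** The SAP calls the figure a proportion with a death event, not a 12-month rate. A reader might infer that the interval has no target at all. It has one, the average risk of a recorded death by the cut, so the coverage table tests a target the SAP never set. This stands, but that target is a by-product of enrolment and follow-up and is of little clinical use.
- **The protocol asks for something close.** Protocol 13.1.1 requires the percentage censored, whose complement is the percentage of deaths. It also attaches two-sided 95% intervals to percentages of categorical variables unless otherwise stated. The first part supports keeping the percentage. The second does not rescue the interval, because the same paragraph gives time-to-event data its own rule.
- **The gap can vanish.** With 24-month accrual, the only enrolment period in the documents, the crude figure is 61% against a true 12-month risk of 60%. A reader might infer that the proportion always understates later mortality; it does not. The agreement is accidental: the same interval almost never covers 6-month mortality.
- **No decision uses it.** Formal testing is confined to the response rate. This stands and sets the weight of the point.

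**Conclusion.** The point holds in a limited form. Beside a sound Kaplan-Meier analysis, the SAP adds a death proportion whose exact interval has no time horizon, and whose value shifts with accrual, loss and cut date while survival stays the same. Under one assumed survival curve (median 9 months), the expected figure at the primary snapshot spans about 38% to 61% across plausible Part 2 accrual lengths. The median, the exponential form, uniform accrual and the accrual lengths are assumptions. That the figure depends on follow-up is not: it follows from the SAP's own censoring and timing rules.

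Two further inferences should be avoided. First, the figure does not move at every planned data release: the update before the NDA (SAP 1.6) covers only response rate and duration of response, so OS is due at the primary and final analyses. Second, extending the model to a cut 14 months after last entry (A = 12) gives 1 − (0.3402 − 0.1350)/0.9242 = 78%, but that overstates the final figure. Follow-up ends 12 months after the last dose, so a patient who stops at month 2 is followed only to about month 14, when the same curve gives 1 − 0.3402 = 66%. The same rule would lower the 61% for 24-month accrual somewhat. Follow-up remains unequal at the final analysis.

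Impact is low. OS is secondary and descriptive in a single-arm trial, and the primary response-rate analysis is unaffected.

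**What to change.** In SAP 4.2.7.2:
- Remove the exact 95% interval from the proportion of deaths.
- Keep deaths as a descriptive n (%), with median follow-up reported beside it. A bare count would go too far, since the protocol already asks for the percentage censored.
- Add Kaplan-Meier survival estimates with 95% intervals (for example Greenwood variance on the log-log scale) at named times such as 6 and 12 months, beside the planned median and curve.
- Report a time point only where follow-up supports it. With 9-month accrual and a cut 2 months after last entry, the longest follow-up is 9 + 2 = 11 months, so a 12-month estimate would have to wait for the final analysis.
- Apply the same rule to the supportive OS analyses.

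The cost is about one SAP sentence and one table row per time point, with the same data and software. Sample size, conduct and the primary analysis do not change.
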